7.6. Protocol deviation

Protocol deviations will be classified into major protocol deviations and minor protocol deviations according to the provisions set in the Protocol Deviation Classification Table. All protocol deviations will be described by classification and degree.

7.7. Selection criteria for subjects included in the analysis and justification

All subjects that meet the inclusion criteria and does not meet the exclusion criteria are considered to meet the requirements for recruitment. The analysis sets in this study are defined as follows:

7.7.1. CCI

CCI

7.7.2. CCI

CCI

7.7.3. CCI

CCI

7.7.4. CCI

CCI

8. Data Management

The individual subject data collected during the trial will be recorded in the corresponding study database. Data will be reviewed by members of the data management team and the corresponding sponsor's study team. For any unexpected or missing data point, a query will be generated and sent to the study site for resolution.

After all subjects complete all follow-up evaluation, database will be locked, and

the data analysis will be performed.

9. Feasibility Analysis

9.1. Possibility analysis on success

The isolation of pulmonary veins (PVI) from the left atrium is the cornerstone for AF ablation procedures. The clinical data from different technologies and catheter designs have shown that PVI is safe and effective in treatment of paroxysmal AF. The BWI PFA system have been proven with features of non-thermal, irreversible, and cardiac tissue selection, which might be used to treat atrial arrhythmias. In pre-clinical studies, it showed that the predicate products were safe and could produce durable lesions.

Although there was limited clinical data about PFA technology in AF ablation, the features of non-thermal and cardiac tissue selection make this technology safer for structures adjacent to the myocardium. So, it is unlikely that the study will be terminated due to safety problems.

The investigational device is provided free of charge, which will not increase the burden of the subjects, so the difficulty in recruiting and screening subjects is acceptable.

9.2. Possibility analysis on failure

Long term effectiveness is unknown for PFA technology. There is limited clinical data for this technology in cardiac ablation area. there may be some undetected problems that may result in some unforeseen results in this study.

Patients will be followed 3 times in clinic and 2 time by phone and have ECG and 24h Holter at 3M/6M/12M follow-ups, which is not SOC and would be challenging in following up.

10. Quality Control of Clinical Trial

During the clinical study, the sponsor and investigator should execute their respective responsibilities according to the *Good Clinical Practice for Medical Device Trials* and applicable relevant Chinese and international regulations. They should also strictly follow the clinical trial protocol, to ensure the quality of clinical trial.

The sponsor should, according to the requirements of the clinical trial protocol, organize the training on the clinical trial protocol and the use and maintenance of investigational product for all investigators participating in the trial, to ensure consistency in the implementation of clinical trial protocol and the use of

investigational products.

During the implementation of study, the sponsor is responsible for monitoring each phase of clinical trial. The clinical monitor designated by the sponsor or designated representative should comply with the relevant SOP and clinical trial protocol that are established by the sponsor to monitor the clinical trial, to ensure the complete, accurate, true, and reliable data.

To ensure the quality of study, the sponsor may authorize the qualified QC or auditor to audit the clinical trial as needed. The investigator should allow the auditors to access to the original data and documents related to this study after receiving the notification.

When the medical products administration or other health administrative authority appoints the inspection personnel to carry out inspection, the study sites and investigators should cooperate and immediately notify the sponsor.

11. Ethical Issues and Informed Consent of Clinical Trial

11.1. Ethical considerations

The study should comply with Chinese laws and regulations, the Declaration of Helsinki and other international consensus, to protect the rights, safety, and health of subjects, including at least the following contents:

- 1) Ensure that the subjects are fully informed and agree to participate in the study voluntarily;
- 2) Respect and protect the privacy of subjects, and keep the records that may identify subjects confidential;
- 3) The production of the investigational medical device should meet relevant requirements of the applicable medical device quality management system; the use of the investigational medical device should meet the requirements of their IFUs, the protocol and relevant operation guidance;
- 4) Select the qualified study sites and investigators;
- 5) A subject has the right to withdraw from the study at any time for any reason without prejudice to their future medical care by the physician or the institution;
- 6) The study protocol and amendment, the ICF and amendment and other study-related applicable documents should be approved by the EC before implementation.

11.2. Approval of trial protocol

Before the trial protocol is submitted to China Food and Drug Administration (if necessary), the EC and other authorities for approval, the internal review and approval should be completed according to the company's SOP.

The clinical trial protocol can be implemented only after the written approval from the EC is obtained.

11.3. Informed consent process

11.3.1. Informed consent process

The written consent of all candidate subjects or their legal authorized representatives must be obtained prior to performing any study operations/procedures (except for SOC operation procedures). Once the investigator determines that the subjects are suitable for participating in this study, the investigator must explain the study background and procedures, possible benefits and risks, etc. to the subjects or their legal authorized representatives. Only the subject who signs the ICF (Informed Consent Form) of the latest version that is approved by the EC (Ethics Committee (EC)) prior to participating in the study is eligible to participate in this study. The subject who does not sign the written ICF is not eligible to participate in this study.

Each subject (or legally authorized representative) must sign and date the ICF of the latest version that is approved by the EC (and other documents as per local regulations) prior to performance of any study-related activity or procedure, that is not standard of care and the study has been fully explained.

The voluntary process of obtaining written informed consent confirms the subject's willingness to participate in the study. The Investigator and/or designee must clearly document the process of obtaining informed consent in the subject clinical record. The investigator has responsibilities to ensure the process of obtaining the informed consent is implemented according to It is the Investigator's responsibility to ensure that the informed consent process is performed in accordance with the *Good Clinical Practice for Medical Device Trials* and relevant regulations, such as Declaration of Helsinki.

12. Device Management

In this study, the sponsor will provide all investigational devices. The package is clearly marked with "For Clinical Trial Only". All devices must be stored according to the conditions specified by the product label and IFU. The principal investigator is responsible for ensuring that the device is properly stored at the site.

The principal investigator or the person designated personnel by the principal

investigator must be responsible for all investigational devices throughout the clinical study and at the end of the study. During the study, the investigational devices must be kept in a locked or safe place. Inventory records of all devices received, used, or returned must be maintained during the clinical trial. The principal investigator must allow the monitor to enter the safe place where the investigational devices are kept in order to check the inventory. At the end of the clinical trial, all unused investigational devices must be returned to Johnson & Johnson Medical (Shanghai) Ltd., and an appropriate investigational device return form must be provided.

12.1. Packaging and labeling of investigational devices

All investigational devices provided by the sponsor in this study are prepared, packaged and labeled by qualified staff or designated personnel of the sponsor in accordance with the company's SOP, Good Manufacturing Practice for Medical Devices (GMP) and relevant local laws/regulations.

The label of each device meets the requirements of guidelines issued by regulatory authorities, GMP, local laws and regulations and company's SOP, and indicates that the investigational product is only for clinical trial.

12.2. Shipment of investigational devices

The sponsor or designated personnel of the sponsor will supply the devices to the study sites according to the device storage conditions in the device IFU.

12.3. Management of investigational devices

The sponsor will be responsible for providing qualified investigational products to the study sites. Each study site should designate related person to be responsible for the management of investigational devices. When the study sites receive the investigational products, they should check the investigational products and ensure that the packages of the investigational products are complete, the quantity is correct, and the transportation conditions meet the requirements.

During the study, the designated person is responsible for recording and counting the usage of the investigational products.

Records related to the receiving, distribution, use, recovery and disposal of investigational products should be kept in accordance with the requirements of Medical Device Good Clinical Practice (MD-GCP).

The investigators should ensure to use the investigational medical device only for the subjects of this clinical trial.

The principal investigator must allow the monitor to enter the safe place where

the investigational devices are kept during the clinical trial in order to check the inventory. At the end of the clinical trial, the unused investigational devices must be returned together with the relevant investigational device return form.

12.4. Return and destruction of investigational devices

All unopened and unused (e.g., expired), opened but unused, damaged, mislabeled or malfunctioning investigational devices should be sent back to the address designated by the sponsor. The corresponding form should be completed, and the devices should be properly returned to the address specified by the sponsor. The appropriate form(s) must be completed, and the device must be returned by courier to an address specified by the sponsor.

13. AEs and Device Complaints reporting

13.1. AEs recording

An adverse event is any untoward medical occurrence, unintended disease or injury, or untoward clinical signs (including abnormal laboratory findings) occurring during a clinical study, whether or not related to the study device or ablation procedure.

The following clinical events will not be considered an adverse event for this clinical study:

- Any medical condition that is present at the time of screening. Such conditions should be added to the medical history if not previously reported. However, if the study subject's condition deteriorates at any time during the study, it should be recorded as an AE.
- Minor pericarditis attributable to the ablation procedure defined as pleuritic chest discomfort with or without pericardial rub and ECG changes.
- A trace/ trivial pericardial effusion that is asymptomatic, requires no medical intervention, and does not extend hospitalization will not be considered an adverse event.
- Postoperative incision pain, fever, incisional scar formation and abnormal lab test values are expected to occur and should not be recorded as AEs unless the investigator considers incision pain, fever, incisional scar formation and abnormal lab test values exceed the normal expected range for postoperative response or are related to the investigational device.

The following clinical events will not be considered an adverse event for this clinical study but will be captured in the database separately:

- Recurrence of pre-existing AF/AT/AFL of unknown origin+
- AF/AT/AFL of unknown origin requiring direct current cardioversion or pharmacological cardioversion (and accompanying hospitalization) during the blanking period. However, new onset of left atrial flutter occurring post ablation is an AE. For subjects with AFL recurrence identified through Holter monitoring; a 12 or 15 leads ECG MUST be collected.
- Re-ablation for AF or pre-existing AT/AFL of unknown origin+ (including accompanying hospitalization) itself is not an AE. However, any complication associated with the repeat ablation procedures is considered an AE and shall be reported within the applicable timelines.

From signing the ICF by the subject, the investigator should determine whether an AE occurs and determine its relationship to the investigational device or procedure at each evaluation for the subjects recruited for the clinical study.

Other AEs, investigational device malfunctions and other product issues must be recorded in the medical record and entered in the e-CRF.

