6.5.5. Repeat Ablation Procedures

Repeat procedures may be performed at the discretion of the investigator. Repeat procedures for AF/AT/AFL of unknown origin⁺ recurrences during the blanking period (90 days post index procedure) must be conducted with the investigational device for ablating PV reconnections. More than 1 repeat procedure for AF/AT/AFL of

unknown origin⁺ during the blanking period is considered a failure mode for primary effectiveness. Procedures for CTI dependent flutter in the follow up period are not considered repeat procedures per protocol.

Repeat procedures performed after the blanking period may be managed per investigator discretion using a commercially available ablation catheter and generator. The follow-up schedule will remain based on the initial ablation procedure.

For the repeat procedures for AF/AT/AFL of unknown origin⁺, investigators must collect and provide information on location of reconnections of PVs and in case of atrial flutter recurrence, confirm if CTI dependent flutter or AFL of unknown origin.

⁺AFL of unknown origin is defined as all AFL except those CTI dependent AFL as confirmed by 12 or 15 leads ECG or entrainment maneuvers in an EP study.

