AEs will be summarized, including the number of AEs and the number and percentage of subjects experiencing any AEs. All PAE, SAEs and all procedure-/device-related AEs will be analyzed in same way. The severity, relationship, AE treatment intervention, seriousness and outcome of all AEs will be described.

In addition, all AEs, PAE, serious and non-serious AEs will be summarized according to the system organ classification and preferred terms of MedDRA, and a list will be generated, including but not limited to subject identification number, age, AE term, start and end time (corresponding duration post procedure), severity, relationship, AE treatment intervention, seriousness, and outcome.

Handling of missing value

Subjects will be contacted by different means, such as by telephone, to avoid missing value.

For the primary endpoint, missing primary endpoint data of the subjects in the FAS will be excluded from the final primary effectiveness analysis as described in “Primary analysis of primary endpoint” of Section 7.5.

For those who had the investigational device inserted but not ablated, they would be replaced, and new subjects should be screened and enrolled to ensure total 110 evaluable non-roll-in subjects.

For baseline information, operational information, or secondary endpoints, all observed data will be used for analysis. Missing data imputation will not be

performed.

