	Possible	The relationship with the study procedure seems relevant and/or the event cannot reasonably be explained by another cause, but additional information may be obtained. Or the relationship with the study procedure is weak but cannot be ruled out completely
	Unlikely	The occurrence of AE is more possibly related to other factors, or the temporal sequence did not reasonably show the relationship between study procedure and the event
	Not related	Relationship to the study procedure can be excluded.

¹ If event is deemed related to procedure, site should indicate whether related to index or repeat if applicable.

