3.2.2 Analysis of secondary effectiveness

All secondary endpoint analyses will be based on RI AT, FAS, and SS AT.

- Acute Procedural Success: the number and percentage of patients with acute procedural success will be calculated, and the two-sided exact 95% confidence interval (CI) will be calculated by the Clopper-Pearson method.
- Acute reconnection: the number and percentage of PVs/subjects with acute reconnection will be calculated, and the two-sided exact 95% confidence interval (CI) will be calculated by the Clopper-Pearson method.
- The number and percentage of PVs/subjects requiring touch-up with a non-study catheter among ablation procedures (including index and repeat ablation procedures); the two-sided exact 95% confidence interval (CI) will be calculated by the Clopper-

Pearson method. Wherein, repeat ablation is defined as any ablation procedure performed after the index procedure, including those recorded during scheduled and unscheduled visits.

- The number and percentage of subjects with repeat ablation procedures during the 12-month follow-up period will be summarized, and the two-sided exact 95% confidence interval will be calculated by the Clopper-Pearson method. The time of repeat ablation (during blanking period, during effectiveness assessment period) and the proportion of PVs/subjects that recovered will be presented. The types of arrhythmias treated with repeated ablation will be presented. Wherein, repeat ablation is defined as any ablation procedure performed after the index procedure, including those recorded during scheduled and unscheduled visits.

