3.3.1 Adverse Event

Adverse events (AEs) will be coded using MedDRA (V25.1 or higher).

The number of adverse events, the number and percentage of subjects with adverse events will be summarized and analyzed based on the RI AS, FAS and SS:

- Any AE

- Occurrence of AEs within 7 days (early-onset) of initial ablation procedure
- Occurrence of AEs within 8-30 days (peri-procedural)
- Occurrence of AEs >30 days (late onset)
- Mild
- Moderate
- Severe
- PAE
 - Ablation catheter-related
 - Generator-related
 - Ablation procedure-related
- SAE
 - Occurrence of SAEs within 7 days (early-onset) of index ablation procedure
 - Occurrence of SAEs within 8-30 days (peri-procedural)
 - Occurrence of SAEs >30 days (late onset)
 - Mild
 - Moderate
 - Severe
- SAE
 - Leading to death
 - Life-threatening illness or injury
 - Requiring hospitalization or prolongation of existing hospitalization
 - Permanent impairment to the body structure or body function
 - Requiring medical measures to prevent permanent impairment to the body structure or body function
 - Leading to fetal distress, fetal death, congenital abnormality or congenital defect
 - Other
- Serious non-primary AE
 - Occurrence of SNPAEs within 7 days (early-onset) of index

ablation procedure

- Occurrence of SNPAEs within 8-30 days (peri-procedural)
- Occurrence of SNPAEs >30 days (late onset)
- Mild
- Moderate
- Severe

- Non-serious AE
 - Occurrence of non-serious AEs within 7 days (early-onset) of index ablation procedure
 - Occurrence of non-serious AEs within 8-30 days (peri-procedural)
 - Occurrence of non-serious AEs >30 days (late onset)
 - Mild
 - Moderate
 - Severe
- Relationship between AE and procedure
 - Definitely unrelated
 - Unlikely related
 - Possibly related
 - Definitely related
- Procedure-related AEs (including: Possibly related and Definitely related)
 - Mild
 - Moderate
 - Severe
- Procedure-related SAEs
- Relationship between AE and ablation catheter
 - Definitely unrelated
 - Unlikely related
 - Possibly related
 - Definitely related

- Ablation catheter-related AEs (including: Possibly related and Definitely related)
 - Mild
 - Moderate
 - Severe
- Ablation catheter-related SAEs
- Relationship between AE and generator
 - Definitely unrelated
 - Unlikely related
 - Possibly related
 - Definitely related
- Generator-related AEs (including: Possibly related and Definitely related)
 - Mild
 - Moderate
 - Severe
- Generator-related SAEs
- AE outcome

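### Procedure-related AE and SAE rows can include complications of post-blanking repeat ablations done with commercial catheters, and no summary table separates them

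*Protocol*

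**What the plan says.** - **Which events are AEs.** Protocol 13.1 does not count a re-ablation itself as an AE, but "any complication associated with the repeat ablation procedures is considered an AE and shall be reported within the applicable timelines". It sets no limit by device or by period.
- **Which device a repeat uses.** Under protocol 6.5.5, repeats for recurrence in the blanking period "must be conducted with the investigational device for ablating PV reconnections". Later ones differ: "Repeat procedures performed after the blanking period may be managed per investigator discretion using a commercially available ablation catheter and generator". The protocol still calls these repeat procedures; it sets aside only procedures for CTI-dependent flutter.
- **What a repeat is.** In SAP 3.2.2, "repeat ablation is defined as any ablation procedure performed after the index procedure". Note 9 to protocol Table 2 gives the same definition.
- **How causality is rated.** Protocol Table 7 (13.2.6) has one category for the device and one for the study procedure. A footnote adds: "If event is deemed related to procedure, site should indicate whether related to index or repeat if applicable".
- **What is tabulated.** Protocol 7.5, under analysis of safety endpoints, says: "All PAE, SAEs and all procedure-/device-related AEs will be analyzed in same way". SAP 3.3.1 has a row labelled "Procedure-related AEs (including: Possibly related and Definitely related", split only by severity, and a single row for "Procedure-related SAEs". It also has SOC/PT tables by relationship to procedure, catheter and generator. The index/repeat flag appears only in the AE listing.
- **What is restricted to the IRE system.** The primary adverse event (PAE) endpoint counts only ablations that use the investigational devices (protocol 6.1.6.1 and 13.2.1, SAP 1.2.3).

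**The concern.** The procedure-related rows are one of the ways a reader will judge the risk of an ablation with the IRE system. There is no control arm to offset events from another source. If complications of a later radiofrequency redo enter these rows, the reported rate depends partly on how many recurrences were re-ablated and with which product. Related SAEs are also a listed safety endpoint (protocol 6.1.6.1 item 3, SAP 1.2.3), so the exposure is not confined to a supporting table.

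The onset windows make a misreading easier, because they run from the index procedure. A complication of a month-6 redo that is rated procedure-related would also be late onset, and so could look like a delayed complication of the IRE ablation. The plan already confines the PAE endpoint to investigational-device procedures. The procedure-related rows have no matching rule.

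**Working it through.** The plan states no figure on this point, so there is none to reproduce. The check has two parts.

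**1. Following one event through the text.** Take a complication of a redo done after day 90 with a commercial catheter.

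1. The redo is a repeat ablation under protocol Table 2 note 9 and SAP 3.2.2.
2. Its complication is an AE under protocol 13.1.
3. Table 7 offers only the study-procedure category for it, and the footnote expects some procedure-related events to be marked as repeat. Nothing visible excludes a commercial-device repeat, and nothing expressly includes one.
4. If the site rates it possibly or definitely related to the procedure, it enters the procedure-related AE row, the SAE row if serious, and the SOC/PT-by-relationship tables. None of these splits by index/repeat or by device.
5. It does not become a PAE on that basis, because the redo did not use the investigational device. It should not enter the catheter- or generator-related rows either.

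**2. Scale.** Inputs:

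- N = 147 subjects at most, of whom 123 are non-roll-in (SAP 1.3.1). The analysis-set definitions are redacted, so the safety denominator is taken as 123 to 147.
- c = 4.5%, the rough major complication rate for RF ablation (protocol 3.1.2), and the only figure given for another device.
- r = share of subjects re-ablated after blanking. This is not in the documents; 5% to 15% is assumed, with every such redo done with a commercial device.

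The formulas are: redos m = N × r; expected affected subjects = m × c; chance of at least one = 1 − (1 − c)^m.

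| r | m (N = 147) | Expected subjects | Chance of at least one |
|---|---|---|---|
| 5% | 7.35, taken as 7 | 7 × 0.045 = 0.32 | 1 − 0.955^7 = 0.276 |
| 15% | 22.05, taken as 22 | 22 × 0.045 = 0.99 | 1 − 0.955^22 = 0.637 |

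Each affected subject adds 1/147 = 0.68 to 1/123 = 0.81 percentage points. The expected addition is r × c: 0.05 × 0.045 = 0.22 points to 0.15 × 0.045 = 0.67 points.

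With wider assumptions (r from 5% to 20%, c from 2% to 8%), the expected addition runs from 0.05 × 0.02 = 0.1 points to 0.20 × 0.08 = 1.6 points. That is 0.15 to 2.35 subjects of 147.

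Two limits apply. A subject already counted for an index-related event does not add to the percentage, so these are upper values for a given r and c. The 4.5% refers to major complications of RF ablation in general. It therefore suits the SAE row better than the row for all AEs, and it may not hold for redos.

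**The case against.** The strongest reply is that Table 7 speaks of the study procedure, and protocol 13.5 asks about the device, medication or surgery specified in the protocol. A discretionary redo with a commercial catheter may not be a study procedure at all. The index/repeat footnote would still make sense for blanking-period repeats with the IRE system alone. This stands to the extent that the mixing is permitted rather than certain. A reader might infer that an RF-redo tamponade at month 6 will be counted as procedure-related; the documents leave that open. The undefined term is itself part of the problem, since sites and analysts would have to decide case by case.

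The second reply is that the main safety evidence is protected. This is correct. A reader might infer that the safety rate of the IRE system as a whole is mixed with that of another product. The documents do not support that: the PAE endpoint is tied to investigational-device procedures and adjudicated by the CEC, and catheter- and generator-related AEs and SAEs have their own rows. One PAE may need a judgement on attribution. PV stenosis counts at any time in 12 months, so it could first appear after a commercial redo. That is a matter for adjudication and is separate from this point.

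Third, a reader might infer that the events cannot be told apart at all. That goes too far. The onset-period tables confine post-blanking redo complications to the late rows, and the listing carries the index/repeat flag and the timing. However, the relationship rows are not crossed with onset, and the items named for the listing do not include the device used in the repeat.

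Finally, the secondary endpoints are descriptive, and any mixing would overstate the risk. Both statements are true. They limit the consequence but do not make the rate interpretable.

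**Conclusion.** The point holds in a limited form. As written, the procedure-related AE and SAE rows and the SOC/PT-by-relationship tables can include complications of post-blanking repeats done with commercial devices, and no summary table would show it. The exposed figures are descriptive, and they include the related-SAE endpoint. No hypothesis test or success criterion changes.

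The effect is modest: 0.3 to 1.0 expected subjects, with a 28% to 64% chance of at least one. This rests on an assumed redo rate of 5% to 15% of 147 subjects, on every such redo using a commercial device, and on roughly 4.5% applying to each. The change is worth making because it is cheap and because, where serious procedure-related events are few, a single misplaced subject is visible.

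**What to change.** 1. In protocol Table 7 and SAP 3.3.1, state whether a repeat ablation with a commercial device counts as a study procedure for causality.
2. In SAP 3.3.1, show procedure-related AEs and SAEs, overall and by SOC/PT, on three lines: related to the index procedure, related to a repeat with the IRE system, and related to a repeat with another device.
3. Derive the lines from the index/repeat flag plus the device recorded for the repeat. The flag alone is not enough, because blanking-period repeats for PV reconnection use the IRE system. The date alone is not enough either, because commercial devices are allowed after blanking but not required. SAP 3.2.2 already analyses non-study-catheter touch-up across index and repeat procedures, so the device appears to be recorded. The CRF is not among the documents, so this should be confirmed.
4. Keep every event in the all-cause AE and SAE totals.

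The cost is SAP wording with a matching clarification to Table 7, a few extra table rows and one derived variable. It needs no extra subjects or visits.
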